Any Grade (Refer to NCI CTCAE applicable version in study protocol for defining the CTCAE grade/severity)	General Guidance Discontinue drug permanently if biopsy- proven immune-mediated myocarditis.	For Any Grade  Initial work-up should include clinical evaluation, B- type natriuretic peptide (BNP), cardiac enzymes, electrocardiogram (ECG), echocardiogram (ECHO), monitoring of oxygenation via pulse oximetry (resting and exertion), and additional laboratory work-up as indicated. Spiral CT or cardiac MRI can complement ECHO to assess wall motion abnormalities when needed.  Patients should be thoroughly evaluated to rule out any alternative etiology (e.g., disease progression, other medications, or infections)
	Any Grade  (Refer to NCI CTCAE applicable version in study protocol for defining the CTCAE	Grade 3-4 Permanently discontinue  Any Grade (Refer to NCI CTCAE applicable version in study protocol for defining the CTCAE

			baseline cardiopulmonary disease and reduced cardiac function.  - Consider discussing with the Clinical Study Lead, as needed.  - Monitor patients for signs and symptoms of myocarditis (new onset or worsening chest pain, arrhythmia, shortness of breath, peripheral edema). As some symptoms can overlap with lung toxicities, simultaneously evaluate for and rule out pulmonary toxicity as well as other causes (e.g., pulmonary embolism, congestive heart failure, malignant pericardial effusion). Consult a cardiologist early, to promptly assess whether and when to complete a cardiac biopsy, including any other diagnostic procedures.  - as indicated. Spiral CT or cardiac MRI can complement ECHO to assess wall motion abnormalities when needed.
	Grade 2, 3 or 4	If Grade 2-4, permanently discontinue study drug/study regimen.	For Grade 2-4  - Monitor symptoms daily, hospitalize.  - Consider cardiology consultation and a prompt start of high-dose/pulse corticosteroid therapy  - Supportive care (e.g., oxygen).  - If no improvement consider additional immunosuppressive therapy such as TNF inhibitors (e.g., infliximab), IVIG or plasmapheresis or other therapies depending on the clinical condition of the patient, based on the discretion of the treating specialist consultant ro relevant practice guidelines. Caution: It is important to rule out sepsis and refer to infliximab label for general guidance before using infliximab. Infliximab is contraindicated for patients who have heart failure.
Myositis Polymyositis	Any Grade (Refer to NCI CTCAE applicable version in study protocol for	General Guidance	For Any Grade  - Patients should be thoroughly evaluated to rule out any alternative etiology (e.g., disease progression, other medications, or infections).

UTSouthwestern Harold C. Simmons Comprehensive Cancer Center

defining the CTCAE grade/sevenity)		Monitor patients for signs and symptoms of poly/myositis. Typically, muscle weakness/pain occurs in proximal muscles including upper arms, thighs, shoulders, hips, neck and back, and; also difficulty breathing and/or trouble swallowing can occur and progress rapidly. Increased general feelings of tiredness and fatigue may occur, and there can be new-onset falling, difficulty getting up from a fall, and trouble climbing stairs, standing up from a seated position, and/or reaching up.
		
 
If poly/myositis is suspected, a Neurology consultation should be obtained early, with prompt guidance on diagnostic procedures. Myocarditis may co-occur with poly/myositis; refer to guidance under Myocarditis. Given breathing complications, refer to guidance under Pneumonitis/ILD. Given possibility of an existent (but previously unknown) autoimmune disorder, consider Rheumatology consultation.
 

		
 
Consider, as necessary, discussing with the Clinical Study Lead.
 

		
 
Consider that patients may present with or progress to rhabdomyolysis. Treat signs and symptoms as per institutional protocol or local clinical practice.
 

		Initial work-up should include clinical evaluation, creatine kinase, aldolase, lactate dehydrogenase (LDH), blood urea nitrogen (BUN)/creatinine, erythrocyte sedimentation rate or C-reactive protein (CRP) level, urine myoglobin, and additional laboratory work-up as indicated, including a number of possible rheumatological/antibody tests (i.e., consider whether a rheumatologist consultation is indicated and could guide need for rheumatoid factor, antinuclear antibody, anti-smooth muscle, antisynthetase [such as anti-Jo-1], and/or signal-recognition particle antibodies). Confirmatory testing may include electromyography, nerve conduction studies, MRI of the muscles, and/or a muscle biopsy. Consider Barium swallow for evaluation of dysphagia or dysphonia.
Grade 1	No dose modifications.	For Grade 1
		
 
Monitor and closely follow up in 2 to 4 days for clinical symptoms and initiate evaluation as clinically indicated.
 

	s	
 
Consider Neurology consult.
 

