		investigator, in discussion with AstraZeneca Clinical Study Lead.  For patients treated with durvalumab in combination with tremelimumab or tremelimumab monotherapy:  A. Permanently discontinue tremelimumab for Grade 3 diarrhea/colitis. HOLD durvalumab until resolution to Grade ≤ 1; durvalumab alone can be resumed after completion of steroid taper (<10 mg prednisone per day or equivalent)  B. Permanently discontinue both durvalumab and tremelimumab for 1) Grade 4 diarrhea/colitis or 2) Any grade of intestinal perforation Grade 4 Permanently discontinue study drug/study regimen.	If perforation is suspected, consult a surgeon experienced in abdominal surgery immediately without any delay.
Hepatitis  Infliximab should not be used for management of immune-related hepatitis.  PLEASE SEE shaded area immediately below this	Any Grade (Refer to NCI CTCAE applicable version in study protocol for defining the CTCAE grade/severity)	General Guidance	For Any Grade     Patients should be thoroughly evaluated to rule out any alternative etiology (e.g., viral hepatitis, disease progression, concomitant medications).     Monitor and evaluate transaminases (aspartate aminotransferase [AST], alanine aminotransferase [ALT], alkaline phosphatase [ALP]) and total bilirubin.
section to find guidance for management of "Hepatitis (elevated LFTS)" in hepatocellular carcinoma	ALT or AST ≤ 3 x ULN or total bilirubin ≤1.5 x ULN	No dose modifications.     If it worsens, then consider holding therapy.	Continue transaminase and total bilirubin monitoring per protocol.
secondary tumour involvement of the liver with abnormal baseline values [BLV])	ALT or AST > 3 ≤ 5 x ULN or total bilirubin > 1.5 ≤ 3 x ULN	Hold study drug/study regimen dose until ALT or AST ≤ 3 x ULN or total bilirubin ≤ 1.5 x ULN. Resume study drug/study regimen after completion of steroid taper (<10 mg prednisone or equivalent).  Permanently discontinue study drug/study regimen for any case meeting Hy's law laboratory criteria (AST or ALT >3 × ULN AND	total bilirubin (e.g., every 1 to 2 days) unti- transaminases and total bilirubin elevations improve or resolve.

		bilirubin ≥2 × ULN without initial findings of cholestasis (i.e., elevated ALP) and in the absence of any alternative cause.	If event is persistent (>2 to 3 days) or worsens, promptly start prednisone 1 to 2 mg/kg/day PO or IV equivalent.

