	ALT or AST > 5- ≤ 10 x ULN	Hold study drug/study regimen. Resume study drug/study regimen if elevations downgrade to ALT or AST ≤ 3 x ULN or total bilimbin ≤ 1.5 x ULN after completion of steroid taper (<10 mg prednisone, or equivalent).      If in combination with tremelimumab, do not restart tremelimumab.	Promptly initiate empiric IV methylprednisolone at 1 to 2 mg/kg/day or equivalent.     Check CPK and aldolase (to rule out myositis)     Perform Hepatology Consult, abdominal workup, and imaging as appropriate.     If still no improvement within 2 to 3 days despite 1 to 2 mg/kg/day methylprednisolone IV or equivalent, promptly start treatment with an additional immunosuppressant (e.g., mycophenolate mofetil 0.5 – 1 g every 12 hours then taper in consultation with hepatology consult or relevant practice guidelines). Discuss with Clinical Study Lead if mycophenolate is not available. Infliximab should NOT be used.
	Concurrent ALT or AST > 3 x ULN and total bilirubin > 2 x ULN  ALT or AST > 10 x ULN OR total bilirubin > 3 x ULN	Permanently discontinue study drug/study regimen.	- Promptly initiate empiric IV methylprednisolone at 1 to 2 mg/kg/day or equivalent If still no improvement within 2 to 3 days despite 1 to 2 mg/kg/day methylprednisolone IV or equivalent, promptly start treatment with an additional immunosuppressant (e.g., mycophenolate mofetil 0.5 – 1 g every 12 hours then taper in consultation with hepatology consult or relevant practice guidelines). Discuss with Clinical Study Lead if mycophenolate is not available. Infliximab should NOT be used.  - Perform Hepatology Consult, abdominal workup, and imaging as appropriate.
Hepatitis  (elevated transaminases and total bilirubin)  Infliximab should not be used for management of immune-related hepatitis.	Any Elevations of AST, ALT, or T. Bili as Described Below	General Guidance	For Any Elevations Described  - Patients should be thoroughly evaluated to rule out any alternative etiology (e.g., viral hepatitis, disease progression, concomitant medications, worsening of liver cirrhosis [e.g., portal vein thrombosis]).  - Monitor and evaluate AST, ALT, ALP, and T. Bili.  - For hepatitis B (HBV) + patients: evaluate quantitative HBV viral load, quantitative Hepatitis B surface antigen (HBsAg), or Hepatitis B envelope antigen (HBeAg).

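### Appendix I releases the >3 to 5 x ULN hepatitis hold on an 'or' condition that an isolated liver-test rise already meets at onset, and the same condition defines the no-change row

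*Combined protocol and SAP*

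**What the plan says.** Section 4.2 sends dosing decisions to Appendix I and tells the investigator to follow the system with the greatest toxicity. In Appendix I, Specific Immune-Mediated Reactions, the Hepatitis rows that apply to this trial (not the shaded rows for liver cancer or liver involvement) run as follows.

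- **No-change row.** Entry: "ALT or AST ≤ 3 x ULN or total bilirubin ≤1.5 x ULN". Dosing is not modified, with the rider "If it worsens, then consider holding therapy".
- **>3 to 5 row.** Entry: "ALT or AST > 3 ≤ 5 x ULN or total bilirubin > 1.5 ≤ 3 x ULN". Action and release: "Hold study drug/study regimen dose until ALT or AST ≤ 3 x ULN or total bilirubin ≤ 1.5 x ULN". Resumption also follows completion of any steroid taper. Prednisone starts only if the event lasts more than 2 to 3 days or worsens.
- **>5 to 10 row.** Entry: "ALT or AST > 5- ≤ 10 x ULN", with no bilirubin term. The drug is held and IV methylprednisolone is started promptly. Release: "Resume study drug/study regimen if elevations downgrade to ALT or AST ≤ 3 x ULN or total bilimbin ≤ 1.5 x ULN", again after a steroid taper.
- **Permanent-stop row.** Entry: "ALT or AST > 10 x ULN OR total bilirubin > 3 x ULN", or an enzyme above 3 x ULN together with bilirubin above 2 x ULN.

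The General Considerations in Appendix I add that steroids are tapered once the event has improved to Grade 1 or lower, over at least 28 days.

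**The concern.** A hold needs a release condition that is false when the hold begins. Here the release is a list of alternatives, and one of them is the test that was never raised. With normal bilirubin, the bilirubin limb is true from the start, whatever the enzymes do; with normal enzymes, the enzyme limb is true whatever bilirubin does. The same limits open the no-change row, so one set of results can point to two different actions.

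The metabolic panel, which includes ALT, AST and bilirubin (section 5.1.11), is drawn at each monthly infusion in consolidation (section 5.4). These rows therefore bear directly on whether that day's dose is given. The first issue is patient safety. The second is that dose delays, and the treatment-delivery compliance reported under section 10.3.4, would depend partly on how the reader takes the connector.

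**Working it through.** The plan gives no figure to reproduce. The check turns the rows into true/false conditions and looks for overlaps.

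**Inputs (x ULN; E = an enzyme, ALT or AST; B = total bilirubin)**

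- No-change: E ≤ 3 or B ≤ 1.5
- >3 to 5 hold: 3 < E ≤ 5 or 1.5 < B ≤ 3
- >5 to 10 hold: 5 < E ≤ 10
- Release limits in both hold rows: E ≤ 3 or B ≤ 1.5, identical to the no-change entry
- Permanent stop: (E > 3 and B > 2) or E > 10 or B > 3

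**Step 1: single cases (ALT = AST)**

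| E | B | No-change row | Other row met | Release limits met at onset |
|---|---|---|---|---|
| 4.5 | 1 | yes | >3 to 5 hold | yes |
| 1 | 2.8 | yes | >3 to 5 hold | yes |
| 8 | 1 | yes | >5 to 10 hold | yes, but see step 4 |
| 12 | 1 | yes | permanent stop | not applicable |
| 4 | 1.8 | no | >3 to 5 hold | no |

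**Step 2: is this general for isolated rises?** ALT and AST were each set at 12 values from 0.5 to 15 and B at 9 values from 0.5 to 5. An isolated rise means that the other test is within its no-change limit.

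- Enzymes raised, B ≤ 1.5: release limits already met in 189 of 189 points in the >3 to 5 row and 189 of 189 in the >5 to 10 row.
- B raised, both enzymes ≤ 3: met in 64 of 64 points in the >3 to 5 row.
- Permanent stop and no-change both met: 132 of 132 isolated enzyme points and 32 of 32 isolated bilirubin points.

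The counts are the same whether *ALT or AST* means either enzyme or the higher one. If the limits are read jointly instead, every overlap falls to 0, so the connector is the cause. That contrast is diagnostic only; it is not a recommendation of that rule.

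**Step 3: a coarse grid of bands.** ALT in {1, 4, 8}, AST in {1, 4, 8}, B in {1, 1.8, 2.5} gives 27 patterns, 26 of them abnormal. With either enzyme counting:

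- Permanent stop (an enzyme > 3 with B = 2.5): 9 − 1 = 8.
- Remaining: 26 − 8 = 18.
- Release limits met at onset: 8 with B = 1, plus 5 with B = 1.8 and at least one enzyme at 1, plus 1 with B = 2.5 and both enzymes at 1; total 14.
- Not met: 18 − 14 = 4 (both enzymes > 3, B = 1.8).

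Of the 14, those with an enzyme at 8 belong to the >5 to 10 row: 5 with B = 1 and 2 with B = 1.8, so 7. The other 14 − 7 = 7 lie in the >3 to 5 row. If the higher enzyme counts, the two of these with one enzyme at 4, the other at 1 and B = 1.8 drop out, leaving 5.

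**Step 4: does other text keep the hold in force?**

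- *>5 to 10 row.* Steroids start promptly, the release speaks of a downgrade, and resumption waits for a taper that begins only after improvement to Grade 1 or lower. The drug does not restart at onset, despite the same connector.
- *>3 to 5 row.* Steroids wait for persistence beyond 2 to 3 days or for worsening. Until then there is no taper to complete, and the release limits are the only barrier.
- *Section 4.2.* It chooses between organ systems. It neither orders the rows within one system nor addresses release.

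**The case against.** The strongest reply is that no sensible investigator would read the table this way. To hold *until* a limit is reached presupposes that the raised test comes down. The >3 to 5 row also asks for repeat tests until the elevations improve or resolve. The General Considerations describe the annex as a recommendation and give a plain ladder from withholding to permanent stop. The study is single-centre, and under section 11.4 medical oncologists review immunotherapy for every patient. Much of this stands: most clinicians would apply each limit to the raised test and follow the worse row. But that rule is not written for rows within one system, and the table uses *and* elsewhere when it wants both tests, so the literal reading cannot be dismissed as loose style.

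Three stronger readings are tempting, and the documents do not support them.

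- A reader might infer that both holds are empty for isolated rises. Step 4 shows that this is wrong for the >5 to 10 row. In the >3 to 5 row the exposure is a window of about 2 to 3 days in a four-weekly regimen.
- A reader might take the hepatitis rates in section 1.3 (12% overall; 4.4% + 0.4% + 0.2% = 5.0% at Grades 3 to 5) and infer 50 x 0.12 = 6 or 50 x 0.05 = 2.5 affected patients. Those would be expected hepatitis cases, not patients in a hold row with an isolated rise, and still less patients given a dose in error.
- A reader might infer that hepatic toxicity grading is distorted. Grading follows CTCAE version 5.0 (sections 4.2 and 7.2.1), not these rows.

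**Conclusion.** The point holds in limited form. As written, the >3 to 5 x ULN hepatitis hold is released by a condition that every isolated enzyme or bilirubin rise in that row already meets, and the same condition places isolated rises of any size in the no-change row alongside a hold or permanent stop. Nothing in section 4.2 resolves the conflict.

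The release fault matters mainly in the >3 to 5 row before steroids start. The 7 of 26 patterns (5 on the higher-enzyme reading) rest on a literal reading of the connector and an arbitrary choice of bands; they describe the logic, not how often it would arise. The number of patients affected cannot be derived from the documents. The sample size and the primary analysis are untouched. It is still worth correcting, because it concerns an infusion-day safety decision and the correction is very cheap.

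**What to change.** Reconcile the Hepatitis rows so that each combination of ALT, AST and bilirubin falls in exactly one row, and so that no hold has a release condition already satisfied by the values that triggered it. Appendix I is a standalone annex versioned independently of the protocol, so the practical place is one clarifying sentence in section 4.2, with the annex wording raised with the drug supplier. The sponsor and drug supplier decide the limits and the clinical rule; this review asks only that the stated rule be consistent. The cost is one sentence in an amendment, with no new tests, visits or patients.

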# UTSouthwestern

Harold C.Simmons Comprehensive Cancer Center

		Consider, as necessary, discussing with the Clinical Study Lead.
Grade 2	
 
Hold study drug/study regimen dose until resolution to Grade ≤1.
 
Permanently discontinue study drug/study regimen if it does not resolve to Grade ≤1 within 30 days or if there are signs of respiratory insufficiency.
 
	For Grade 2  Monitor symptoms daily and consider hospitalization.  Consider Rheumatology or Neurology consult, and initiate evaluation.  Consider, as necessary, discussing with the Clinical Study Lead.  If clinical course is rapidly progressive (particularly if difficulty breathing and/or trouble swallowing), promptly start IV methylprednisolone 2 to 4 mg/kg/day systemic steroids along with receiving input from Neurology consultant  If clinical course is not rapidly progressive, start systemic steroids (e.g., prednisone 1 to 2 mg/kg/day PO or IV equivalent); if no improvement within 2 to 3 days, continue additional work up and start treatment with IV methylprednisolone 2 to 4 mg/kg/day  If after start of IV methylprednisolone at 2 to 4 mg/kg/day there is no improvement within 3 days, consider additional  immunosuppressive therapy such as TNF inhibitors (e.g., infliximab), IVIG or plasmapheresis, or other therapies based on the discretion of the treating specialist consultant or relevant practice guideline Caution: It is important to rule out sepsis and refer to infliximab label for general guidance before using infliximab.
Grade 3	For Grade 3  - Hold study drug/study regimen dose until resolution to Grade ≤1.  - Permanently discontinue study drug/study regimen if Grade 3 imAE does not resolve to Grade ≤1 within 30	hospitalization.  — Consider Rheumatology and/or Neurology consult
	days or if there are signs of respiratory insufficiency.	
 
If after start of IV methylprednisolone at 2 to 4 mg/kg/day there is no improvement within 2 to 3 days, consider starting another immunosuppressive therapy such as a TNF inhibitor (e.g., infliximab at 5 mg/kg IV, may be repeated at 2 and 6 weeks after initial dose at the discretion of the treating provider or relevant practice guidelines). Caution: It is important to rule out sepsis and refer to infliximab label for general guidance before using infliximab.
 
Consider whether patient may require IV IG, plasmapheresis.
 

Grade 4	For Grade 4  Permanently discontinue study drug/study regimen.	Monitor symptoms closely; recommend hospitalization.  Consider Rheumatology and/or Neurology consult Consider discussing with the Clinical Study Lead, as needed.  Promptly start IV methylprednisolone 2 to 4 mg/kg/day systemic steroids along with receiving input from Neurology consultant.  If after start of IV methylprednisolone at 2 to 4 mg/kg/day there is no improvement within 2 to 3 days, consider starting another immunosuppressive therapy such as a TNF inhibitor (e.g., infliximab at 5 mg/kg IV, may be repeated at 2 and 6 weeks after initial dose at the discretion of the treating provider or relevant practice guidelines). Caution: It is important to rule out sepsis and refer to infliximab label for general guidance before using infliximab.

<sup>1 SCAR terms include Stevens-Johnson Syndrome (SJS), Toxic Epidermal Necrolysis (TEN), Erythema Multiforme, Acute Generalized Exanthematous Pustulosis, Drug Reaction with Eosinophilia and Systemic Symptoms (DRESS) and Drug-induced hypersensitivity syndrome.

#### Other-Immune-Mediated Reactions

Severity Grade of the Event Refer to NCI CTCAE applicable version in study protocol for defining the CTCAE grade/severity)	Dose Modifications	Toxicity Management
Any Grade	Note: It is possible that events with an inflammatory or immune mediated mechanism could occur in nearly all organs, some of them are not noted specifically in these guidelines (e.g. immune thrombocytopenia, haemolytic anaemia, uveitis, vasculitis).	Patients should be thoroughly evaluated to rule out any alternative etiology (e.g., disease progression, other medications or infections).  The Clinical Study Lead may be contacted for immune-mediate reactions not listed in the "specific immune-mediated reactions' section  Consultation with relevant specialist  Treat accordingly, as per institutional standard.
Grade 1	No dose modifications.	Monitor as clinically indicated
Grade 2	Hold study drug/study regimen until resolution to ≤Grade 1 or baseline.      If toxicity worsens, then treat as Grade 3 or Grade 4.      Study drug/study regimen can be resumed once event stabilizes to Grade ≤1 after completion of steroid taper.      Consider whether study drug/study regimen should be permanently discontinued in Grade 2 events with high likelihood for morbidity and/or mortality when they do not rapidly improve to Grade <1 upon treatment with systemic steroids and following full taper.	For Grade 2, 3, or 4  Treat accordingly, as per institutional standard, appropriate clinical practice guidelines, and society guidelines. (See page 4).
Grade 3	Hold study drug/study regimen until resolution to Grade ≤1 or baseline	
Grade 4	Permanently discontinue study drug/study regimen	

Note: As applicable, for early phase studies, the following sentence may be added: "Any event greater than or equal to Grade 2, please discuss with Clinical Study Lead."

# Infusion-Related Reactions

Severity Grade of the Event (Refer to NCI CTCAE applicable version in study protocol for defining the CTCAE grade/severity)	Dose Modifications	Toxicity Management
Any Grade	General Guidance	For Any Grade  Manage per institutional standard at the discretion of investigator.  Monitor patients for signs and symptoms of infusion-related reactions (e.g., fever and/or shaking chills, flushing and/or itching alterations in heart rate and blood pressure, dyspnea or chest discomfort, or skin rashes) and anaphylaxis (e.g., generalized urticaria, angioedema, wheezing, hypotension, or tachycardia).
Grade 1 or 2	For Grade 1  The infusion rate of study drug/study regimen may be decreased by 50% or temporarily interrupted until resolution of the event.  For Grade 2	For Grade 1 or 2      Acetaminophen and/or antihistamines may be administered per institutional standard at the discretion of the investigator.      Consider premedication per institutional standard or study protoc prior to subsequent doses.      Consider steroids for patients who have previously experienced infusion reaction; use of steroid premedication may be permitted in these situations
	The infusion rate of study drug/study regimen may be decreased 50% or temporarily interrupted until resolution of the event.  Subsequent infusions may be given at 50% of the initial infusion rate.	
Grade 3 or 4	For Grade 3 or 4 Permanently discontinue study drug/study regimen.	For Grade 3 or 4  Manage severe infusion-related reactions per institutional standar appropriate clinical practice guidelines, and society guidelines.

